ESOM_NF, Emotional-Self-Other Morph Neurofeedback
ESOM-Pre, ESOM task presented before ESOM_NF task
ESOM-Post, ESOM task presented after ESOM_NF task
ER; Emotion Regulation Task;
FC; functional connectivity
IAT, Implicit Association Test;
IMM; Independent Medical Monitor;
MDD: Major Depressive Disorder;
mPFC, Medial Prefrontal Cortex;
mPFC FC; medial prefrontal cortex functional connectivity
NF, Neurofeedback;
QR; Quick Response Code
ROI, region of interest;
PTSD: Post Traumatic Stress Disorder;
Personal Health Information: PHI
UMN: University of Minnesota

1. Objectives

R61 Phase Specific Aims: Given the modest efficacy of current evidence-based treatments ¹⁻⁷, novel, personalized interventions for adolescent suicide behaviors are needed. Repeated suicide attempts are predicted by abnormal self-processing and affect dysregulation ^{4,8-13}. Abnormal self-processing is neglect of positive self-relevant information and excessive focus on negative information. Self-processing (e.g., self-face recognition) is enabled by the dorsal anterior cingulate cortex (**dACC**) ¹⁴⁻¹⁶ and medial prefrontal cortex (**mPFC**) ⁴⁰⁻⁴. Those neural hubs enable awareness of salient stimuli ¹⁷ and affect regulation, which is modulation of emotions borne by neural hubs such as the **amygdala** ¹⁸. Adolescence is a neuroplastic period for the circuits of affect regulation and self-processing ^{19,20}. It is unknown whether engaging those circuits using novel interventions could reduce suicide risks, e.g., suicide ideation. To begin to address this knowledge gap, in the R61 phase we will test the efficacy of neurofeedback training to engage the neurocircuitry of self-processing and emotion regulation (dACC, mPFC and amygdala) in 1st time suicide attempting Participants.

To establish target engagement, **in the R61 phase**, participants will be trained to increase the activity of one of two competing neural hubs ($N_{dACC}=20$ or $N_{Right-Amygdala}=20$). We will identify which circuits are better engaged during and after NF in time suicide attempting participants (11-18 years) with current suicide ideation as well as 17 – 45 y.o participants with symptoms of borderline personality disorder. Behavior and circuits of affect regulation and self-processing will be sampled before and after two NF training sessions.

The **R61 milestones for proceeding to the R33 phase are:**

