Milestone 1: NF loci (dACC or amygdala) must show higher activity during ESF-NF and higher FC with mPFC after NF training during the ESOM or ER tasks with effect sizes of $d \geq 0.4$.

Milestone 2: 20% of variance in psychological target's change (ETB, IAT) must be associated with amygdala or dACC to mPFC FC changes during the ESOM or ER tasks after NF.

If those milestones are met, during **the R33 phase**, 70 suicide attempting participants with pre-NF assessments will be randomized 1:1 to: NF or NF from a region that is not related to memory recall, labeled as "Unrelated-NF". Participants will be matched in sex, age, IQ, illness severity, suicide ideation, and abuse history if possible. Leveraging Bayesian methods to increase power, our aims and hypothesis (**H**) for the R33 phase are:

R33 Aim 1. Confirm target engagement in the NF versus the Unrelated-NF group.

H1.1: Right amygdala or dACC activity will be higher for active versus Unrelated-NF.

H1.2: Right amygdala or dACC – mPFC FC will be higher during self-processing and affect regulation tasks following active NF compared to Unrelated-NF training sessions.

R33 Aim 2. Test the relationship between neural and psychological targets' engagement and suicide ideation. H2.1: Lower affect dysregulation and abnormal self-processing behavior will follow active NF as compared to Unrelated-NF, mediated by amygdala or dACC to mPFC FC changes in self-processing and affect regulation tasks. H2.2: Higher amygdala or dACC to mPFC FC after NF will be associated with lower suicide ideation. H2.3: Affect dysregulation or abnormal self-processing behavioral changes will mediate the association between changes in FC and suicide ideation before versus after NF.

2. Background

Suicide is the 2nd leading cause of adolescent death in the U.S ²¹. Yet it is increasingly acknowledged that current evidence-based interventions for illnesses linked to suicide ideation and attempts underperform across the lifespan ^{1-7,22}.

3. Study Endpoints/Events/Outcomes

3.1 Primary Endpoint/Event/Outcome:

The primary outcome of the R61 stage will be the fMRI imaging results, behavioral tasks (IAT and EBT) and self-reported suicide ideation data. The DERS²³, RD¹²⁰ and the SPPA^{24,25} will provide self-report measures of affect dysregulation and abnormal self-processing. **The primary outcomes of the R33 stage** are similar as above but now include the C-SSRS⁹⁸ and SIQ²⁹ to test changes in suicide ideation and attempts

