Description. Neurofeedback training is a modality of biofeedback. During neurofeedback training, a person that is inside the scanner can see the changing levels of activity of a selected brain region. Because regional neural activity is visually displayed to a person in the scanner, this enables voluntary modulation of neural activity in regions of interest, which can trigger corrective neuroplastic processes. We will deliver neurofeedback training using the **Emotional Self-Face Neurofeedback, ESF-NF paradigm**^{30,31} comprised by four ~7.33 min NF training runs preceded by a 5 min baseline (ESF no NF), a 5 min practice run, and followed by a 5 min transfer run (ESF no NF)³². Training entails NF blocks paired to a self-happy face visual that signals the start of NF. There will be two control conditions to distract participants from contemplating positive memories and dampen affect regulation and self-processing networks. During one control condition participants will count backwards from 100 cued by an unfamiliar happy teen face with no NF (count backward = **CB**). During other control condition participants are presented with the cue "Rest" and are asked to relax and look at the screen (**Rest**). During **NF**, participants will attempt to increase neural activity displayed via a colored bar shifting up or down depending on values provided by MURFI2 software³³. Green = Activity > baseline and red = Activity < baseline. We may adapt the feedback procedures to be more like a game, but the current description still conveys the visual feedback modality. The active NF loci will be the right amygdala or the dorsal ACC in the R61 phase. The active NF loci during the R33 phase will be the loci of higher engagement that best elicits functional improvements in the R61 phase. As in prior NF trials³⁴⁻³⁶, participants select positive autobiographical memories that they recall during NF training. **[name]** has administered a short version of the proposed task to 53 Participants^{30,31}. ROIs for the dACC, right amygdala or an unrelated site (e.g., the left intraparietal sulcus) will be localized from coordinates mapped to each participant's structural image. **[name]** has used this software and protocol with healthy and depressed participants^{30,31}. The scanning room and specifically the scanner coils already include devices to present stimuli. It is part of the hardware. We may monitor heart rate and breathing using devices that are superficially attached to the participant's torso. These devices are also often used as part of scanning procedures of human participants.

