Visit 1: Baseline	Visit 2: Scan day 1	Visit 3: Scan day 2	Visit 4: Post-NF	Visit 5: Approximately 1 Month later after Visit 4.	Additional visits as needed to complete pending tasks
KSADS. Children Depression Rating Scale-Revised (CDRS). Difficulty with Emotion Regulation Scale (DERS) ²³ . Self-Perception Profile for Participants (SPPA) ^{24,25} . Responses to Depression (RD) ⁴⁸ : rumination.	SIQ, BDI, DERS, SPPA, RD Medication, psychotherapy. Review 5 happy memories.	SIQ, BDI, DERS, SPPA, RD Review 5 happy memories.	SIQ, BDI, DERS, SPPA, RD.	SIQ, BDI, DERS, SPPA, RD Online	Anything pending
Columbia-Suicide Severity Rating Scale, C-SSRS, ⁴⁹ . Suicide Ideation Questionnaire, SIQ ²⁹ .	ESOM: 14 min ER: 13 min	NF Training: ESF_NF ~ 44.32 min	C-SSRS, CDRS	KSADS-COMP and C-SSRS	Anything pending
Beck Depression Inventory, BDI ²⁷ . Child Trauma Questionnaire, CTQ ²⁸	NF Training: ESF_NF~ 44.32 min	ESOM: 14 min ER: 13 min	IAT and ETB		Anything pending
Wechsler Abbreviated Scale for Intelligence, WASI ⁵⁰ . Edinburgh handedness inventory. Write/ discuss 5 happy memories.	30 min break	30 min break	Medication, psychotherapy	Medication and psychotherapy	Anything pending
Medication, psychotherapy, demographics, and puberty stage⁵¹.					Anything pending
Implicit Association Test (IAT): Abnormal Self-Processing Behavior ^{38,39} . Emotional Testing Battery (ETB): Affect and self-processing ⁴⁰ , or another similar test. Can be administered also before scanning on scan day 1 or after scanning on scan day 2.	Ease of recall rating. SIQ, BDI, DERS, SPPA, RD.	Medication, psychotherapy. Ease of recall rating. SIQ, BDI, DERS, SPPA, RD.		IAT and ETB	Anything pending

- Items from the KSADS, C-SSRS and Medication and psychotherapy forms will be shared with the IMM to confirm inclusion vs. exclusion of participants.

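### R61 asks which of two neurofeedback loci is better engaged, but no stated R61 analysis compares the arms, and Milestone 1 alone does not show a feedback-specific effect

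*Combined protocol and SAP*

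**What the plan says.** - **Aim (section 1).** Participants are trained on one of two competing hubs, 20 on the dACC and 20 on the right amygdala: "We will identify which circuits are better engaged during and after NF".
- **Milestone 1 (section 1).** The trained locus "must show higher activity during ESF-NF and higher FC with mPFC after NF training during the ESOM or ER tasks", with d of at least 0.4.
- **Use of the answer (section 4).** "The active NF loci during the R33 phase will be the loci of higher engagement that best elicits functional improvements in the R61 phase".
- **Task (section 4).** "Training entails NF blocks paired to a self-happy face visual that signals the start of NF", and "participants select positive autobiographical memories that they recall during NF training". In one control condition "participants will count backwards from 100 cued by an unfamiliar happy teen face with no NF"; in the other, participants rest.
- **Session structure (section 4).** There are "four ~7.33 min NF training runs preceded by a 5 min baseline (ESF no NF), a 5 min practice run", then a 5 min transfer run, also without feedback.
- **Activity analysis (section 18).** Single-sample t-tests of NF vs CB and NF vs Rest, with the same tests run separately on the baseline and transfer runs.
- **Connectivity analysis (section 18).** A mixed-effects ANOVA whose only named factor is time, at thresholds similar to those for activity. Causal modelling and correlations with behaviour follow.
- **Allocation.** Section 29.1 describes random assignment between the two R61 loci. The Data Integrity paragraph of section 18 mentions random assignment for R33 only.

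**The concern.** The aim is comparative and the allocation supports a comparison, but the analysis section contains none. Followed exactly, the plan gives two per-locus effect sizes and no interval for their difference. The engagement part of the R33 locus choice would rest on those two numbers.

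Milestone 1 has a second limit. NF blocks differ from both control conditions in mental task and cue as well as in feedback. Section 5.1 describes both regions as enabling memory recall, and section 1 links the dACC to self-face recognition, so some target activity could arise without feedback. A pre/post connectivity change could come from practice or time.

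At stake are how the go decision is read, the locus choice, and any R33 prior built from these single-arm effects, since section 18 allows R61 results to adjust the R33 models.

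**Working it through.** **1. The plan's own power figure.** Section 18 gives 80% power at d = 0.49 for one locus with 20 per locus; it states no alpha or sidedness for this. One-sample noncentral t, n = 20, d = 0.49 (noncentrality 0.49 × √20 = 2.19):

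| Assumed alpha | Power |
|---|---|
| two-sided 0.05 | 0.55 |
| one-sided 0.05 | 0.68 |
| one-sided 0.10 | 0.81 |

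The figure is reached only with an alpha that the plan does not state. Either way it concerns one locus and says nothing about a between-locus difference.

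**2. Is an arm contrast stated anywhere for R61?**

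| R61 analysis (section 18) | Compares arms? |
|---|---|
| Single-sample NF vs CB, NF vs Rest | No, within locus |
| Same tests on baseline and transfer runs | No; no contrast with NF runs either |
| Connectivity ANOVA | Time is the only named factor |
| Causal modelling, correlations | No |

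**3. What differs between the conditions?**

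| Element (section 4) | NF block | CB | Rest |
|---|---|---|---|
| Feedback | yes | no | no |
| Positive recall | yes | no (counting) | no |
| Face cue | own, happy | unfamiliar, happy | none (word cue) |

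Feedback changes together with recall and face, so neither contrast isolates it.

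**4. Is there a no-feedback run in each session?** 4 × 7.33 + 3 × 5 = 44.32 min. This matches Table 1 for the second scan day ("NF Training: ESF_NF ~ 44.32 min"), and the first scan day shows the same duration. So there is a baseline run in each session, and the one in session 1 precedes all training.

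**5. Precision of a between-arm contrast.** Assumptions: 20 v 20, two-sided 0.05, common SD.
- SE = √(2/20) = 0.316 SD, against √(1/20) = 0.224 SD for one arm.
- 95% half-width = 2.024 × 0.316 = 0.64 SD.
- d for 80% power = 0.91. With ANCOVA and an assumed baseline correlation of 0.5 it is 0.91 × √(1 − 0.25) = 0.79.
- Power at d = 0.4 is 23%.

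**6. Choosing the larger observed own-target d.** 400,000 draws, n = 20 per arm. The chance that the interval includes zero is Φ(1.96 − δ/SD) − Φ(−1.96 − δ/SD), where δ is the true gap.

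| True d | SD of difference | Better locus chosen | Interval includes 0 |
|---|---|---|---|
| 0.37 v 0.324 (pilot) | 0.346 | 56% | 95% |
| 0.6 v 0.4 | 0.358 | 72% | 91% |
| 0.9 v 0.4 | 0.377 | 92% | about 74% |

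**7. Illustration: Milestone 1 with zero feedback effect, before Milestone 2.** The documents give no no-feedback effect size and no connectivity change without NF, so both are assumed. With n = 20, P(observed d ≥ 0.4) is 0.458, 0.381, 0.184, 0.159 and 0.045 at true d 0.37, 0.324, 0.185, 0.162 and 0. For connectivity in either of two tasks (independent), 1 − (1 − p)² gives 0.088, 0.362 and 0.759 at true d 0, 0.2 and 0.4.

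Example, upper end: amygdala 0.458 × 0.759 = 0.348; dACC 0.381 × 0.759 = 0.289; at least one = 1 − 0.652 × 0.711 = 0.54.

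| Share of pilot d due to recall or own face | Connectivity d 0 / 0.2 / 0.4 | Same, with p < 0.01 on activity and connectivity |
|---|---|---|
| None | 0.8% / 3% / 7% | not tabulated |
| Half | 3% / 12% / 24% | 0.06% / 0.5% / 2% |
| All | 7% / 28% / 54% | 0.25% / 2% / 8% |

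The p rule is approximated as a two-sided t-test, which needs an observed d ≥ 0.64. With correlation 0.5 between measures (100,000 simulations), the half-to-all range with the p rule is about 0.5–15%.

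**The case against.** **Feedback specificity is R33's job.** This stands. R33 Aim 1 compares active with Unrelated-NF, and nothing here weakens that comparison. A reader might infer that the programme cannot show a feedback effect; the documents do not support that. The limit applies to Milestone 1 and to what R61 is said to establish.

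**R61 is not without a reference.** This also stands. A reader might infer that the data can say nothing about feedback within an arm. Baseline and transfer runs without feedback exist and section 18 tests them. What is missing is any contrast with the NF runs, and that contrast would be confounded with order and run length.

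**A mixed-effects ANOVA could carry an arm factor.** It could, but none is named.

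**Selecting the larger estimate is legitimate.** It is, and section 4 adds functional improvement as a criterion. An interval will usually include zero and will not raise the chance of a correct pick. The point is to report the choice as a selection.

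**The false-go figures are soft.** This stands. A reader might take 54% as the risk of a wrong go decision. That needs the whole pilot effect to be recall or own-face response, plus a non-NF connectivity change equal to the milestone threshold. It also ignores Milestone 2 and any p rule.

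**The number of R61 arms is not settled everywhere.** Sections 1, 18 and 29.1 describe two loci and 40 participants. Section 11.1 gives a minimum of 60 at 20 per target, which would fit three groups arithmetically. Two arms is the better-supported reading, but the passages need reconciling.

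**Conclusion.** The point holds as a gap between aim and analysis. R61 poses a comparative question and allocates participants so that it can be addressed, yet states no arm contrast. Milestone 1 alone does not separate feedback from recall, own-face viewing, practice or time.

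The firmest numbers are those on precision and selection. They assume 20 per arm and a common SD, and need no assumption about confounding: half-width about 0.64 SD, 80% power only at d of about 0.91, and a correct pick in 56% of trials at the pilot gap. R61 may therefore be unable to separate the loci, and the added contrasts are estimates, not powered tests.

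The Milestone 1 figures are illustrative only: about 1–7% with no recall or own-face effect, 3–54% under the stated range of assumptions with independent measures, and about 0.06–8% for that same range if p < 0.01 is also required for activity and connectivity. They show that the answer depends on an effect the plan does not isolate; they do not measure the go-decision error. The change should be made, but it does not block the trial.

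**What to change.** In the R61 part of section 18:

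1. **Primary between-arm contrast, for each region.** ANCOVA of NF-run activity (NF vs CB), trained arm against other arm, adjusted for the session 1 no-feedback baseline run. Randomisation then balances recall and own-face viewing. NF vs Rest is supportive.
2. **Connectivity, secondary.** Add arm and arm-by-time to the ANOVA, fitted separately for dACC–mPFC and right amygdala–mPFC, in ESOM and in ER.
3. **The better-engaged question.** Report the between-arm difference in standardised own-target engagement with its 95% interval. Note that it still contains each region's response to recall and own face.
4. **Supportive only.** Training-run minus baseline-run, because order and run length differ (about 7.33 v 5 min).
5. **Interpretation, stated in advance.** The R33 locus is a selection, made on the larger engagement estimate together with section 4's functional-improvement criterion. It is not a demonstrated difference unless the interval in item 3 excludes zero. Milestone 1 alone is not evidence of a feedback-specific effect. The d ≥ 0.4 go rule is unchanged.
6. **Reconcile.** Confirm R61 randomisation in section 18, and align the 60 in section 11.1 with the 40 in sections 18 and 29.1.

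The cost is SAP wording and a few contrasts on data already collected, with no new visits or participants. The arm contrast is less precise than the single-sample test (SE 0.32 v 0.22 SD). It is also conservative, because the other arm is active too.

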Implicit Association Test, IAT^{38,39}. A computer-based test that uses reaction times for word classifications to measure self-relevant associations about life and death/suicide. Participants will classify stimuli representing the constructs of "death" (i.e., die, suicide) and "life" (i.e., alive, thrive) and the attributes of "me" (i.e., I, myself, self) and "not me" (i.e., theirs, other). RTs are recorded and an IAT score indexes association between "death" and "me." A positive IAT score indicates stronger association between death and self (i.e., faster RT to the "death"/"me" blocks vs. "life"/"me" blocks). A negative IAT score indicates stronger association between life and self^{38,39}.

Emotional Testing Battery, ETB⁴⁰. The ETB is comprised of computerized tasks that assess emotional processing and affect regulation. The facial expression recognition test (**FERT**) entails recognizing six different facial expressions of varying intensity in random order. It yields accuracy and reaction times across positive and negative expressions. The emotional categorization task (**ECAT**) tests response speed to positive and negative self-descriptors that participants categorize as something they would like or dislike to overhear someone saying they possess. Reaction times for positive descriptors are the outcome. The emotional recall task (**ERT**) takes place 15 mn after the ECAT. Participants recall as many descriptors as possible. Recall accuracy and intrusions of positive vs. negative descriptors are the outcomes. The faces dot-probe tasks (**FDOT**) present images of emotional or neutral faces followed by a probe to select the correct orientation of the faces (vertical vs. horizontal). Faces are presented as either masked, i.e., too fast for conscious processing, or un-masked. The outcome is vigilance scores calculated by subtracting reaction times from trials with probes in the same positions as faces (congruent) from trials where probes appeared in opposite positions as faces (incongruent).

Table 1 (11-18 years old). Patients with BPD (17-45 years old) **may complete only 4 sessions.** Several weeks may separate visits and additional visits may be scheduled to complete unfinished procedures. Order and day of procedures administration can be altered by adding additional visits or flexibly to accommodate participant's needs.

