Data Analysis Plan. SPM12 ⁵⁵ will be used for fMRI statistical analyses. EPI time series' preprocessing will include: (1) realignment for motion correction, (2) slice timing correction, (3) co-registration of EPI with anatomical data, (4) spatial normalization to MNI anatomical, and (5) spatial smoothing. Head motion outliers in EPI time series will be corrected using the Artifact Detection Tools with a scan-to-scan movement threshold of 0.2 mm and a scan-to-scan global signal change of 3 SD ⁵⁶. Activity. For each subject, BOLD activity contrast signal variance will be modeled with regressors using a General Linear Model (GLM) to generate 1st level contrasts (NF vs. CB and NF vs. Rest) for the ESF-NF task similar to procedures followed by Young et al. ³². [name] will lead activity analyses. Connectivity. Time series in dACC or right-amygdala for the ESOM and ER tasks will be used to yield general psychophysiological interaction (gPPI) contrast variables ⁵⁷. The gPPI variables represent FC differences for 'self' vs. 'other' faces recognition or 'regulation' vs. 'passive' viewing. The processing pipeline configuration will be available online. The research staff and a software programmer will generate automatic pre-processing scripts using pilot adult data to yield 1st level images for both activity, connectivity, and structural data to ensure rapid quality control and data access. General PPI analyses yield information flow between neural nodes without direction of exchange. Competing models of affect valuation versus affect modulation/suppression assume 'bottom-up' influence from amygdala on mPFC or 'top-down' influence from the mPFC and dACC on the amygdala, respectively⁵⁸. Dynamic causal modeling (DCM)⁵⁹⁻⁶¹ will follow up gPPI analyses to test bottom-up vs. top-down models of information flow between target neural hubs. DCM will also test FC patterns during NF training but increase target activity during NF is the key target for our Milestone 1. [name] will conduct FC analyses and determine how functional neuro-architecture of affect regulation and self-processing changes after NF training. Defining ROIs. In line with our focus on amygdala, dACC, and their connectivity with mPFC, we will target the dACC (MNI: x=-8, y=30, z=30), the highest loci of activity within the ACC in our pilot results and the right amygdala (MNI x=28 y=0 z=-19), the loci of our amygdala-ACC FC results in attempting participants ⁴¹. ROIs of activity (5 mm) centered in those coordinates during NF, and their FC to mPFC (polar aspects of BA10-9) during ER and ESOM tasks are the target ROIs. The unrelated locus is the left horizontal segment of the intraparietal sulcus (MNI x=-42 y=-48 z=48). This region is not involved in emotion regulation or self-processing and has been used before as a locus of Unrelated comparison NF ^{32,34-36}. Finally, our decision of using specific coordinates, instead of localizing ROIs with a task that elicits dACC or amygdala activity, is supported using pre-determined coordinates for NF in research that yielded ROI up-regulation and symptoms improvement ^{32,34-36}. Accordingly, we have selected coordinates based on our published and pilot work. Puberty ⁵¹, illness or depression (BDI) severity, treatment indexes, substance use, IQ, handedness, or any variable differing between key groups will be covariates in all analyses.

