
Power Analysis: Power and R61 Milestones. With N=40 (20 per NF's loci), the R61 phase yields 80% power to detect an effect size of $d=0.49$ for one of the loci. Our data yielded statistically significant effect sizes of dAmygdala=0.37 and ddACC=0.324 in activity increases during a short version of the proposed ESF-NF task. Longer NF duration yield effect sizes as large as $d= 1.2$ as shown by Young et al. ^{32,34-36}. Since we focus on target circuitry identified by prior studies, we will employ region of interest (ROI) for connectivity and activity analyses in the R61 phase.

Statistical Analysis: Milestone (1-2) tests: Neural targets' activity (dACC or Amygdala) during NF will be tested using 1st-level NF vs. CB similar to Zotev et al. ³⁶ and NF vs. Rest, similar to Young et al. ^{32,34-36} in single-sample t-tests (p-corrected, 0.01 using the AFNI program 3dClustSim voxel-level threshold of $p<0.001$) to identify regional effects controlling for key covariates noted in C3.2 for the ROIs and to estimate effect sizes during the ESF-NF task. Tests proposed for the ESF-NF task will be also conducted with the baseline and transfer runs to establish baseline (pre-NF) and post-treatment engagement of the neural targets. Neural targets' connectivity after NF. NF training effects in self-processing and affect regulation neural circuits during the ESOM and ER tasks, will

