We will use a University secure desktop or laptop not previously listed to analyze and **store completely de-identified databases**. These databases will be purged of all participant's identifying information from the beginning. An age-calculator will be used to de-identify participants' date of birth while still maintaining an accurate age (in terms of months and years) for all collection points. We must include age in all analysis to control for developmental differences in brain maturation, thus de-identified age at each sampling point must be included in all databases and analysis.

I will use external hard drives or USB drives ("flash" or "thumb" drives) not previously listed to analyze and store completely de-identified data bases. These databases will be purged of participant's identifying information from the beginning; they will be completely de-identified and contain no participant PHI. To track participants' age in a de-identified manner, an age calculator will be used to create a transformed date of birth (ex. with a randomly generated jittering number that shifts the date of birth -/+6 months).

I will use a mobile device such as a tablet or smartphone not previously listed to analyze and store completely de-identified databases. These databases will be purged of all participant's identifying information from the beginning. All databases will be completely de-identified which means all databases will lack all participants' PHI and contact information.

Please note that in the above devices (tablet, smartphone, laptops) ONLY completely de-identified will be kept within the PI's Google drive which is only accessible with the PI's password and/or expressed access granted by the PI. It is not possible to analyze, depict or work with the data without having de-identified databases that are shared with students or collaborators.

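### Milestone 2 (20% of variance) requires no sign, no common locus with Milestone 1 and no named score, so once Milestone 1 is met it adds little evidence of an FC–behaviour link

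*Combined protocol and SAP*

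**What the plan says.** Section 1 (Objectives, R61 milestones) sets two milestones and opens R33 with "If those milestones are met". Milestone 1 asks for higher activity during training and higher FC with mPFC afterwards, each with d of at least 0.4. Milestone 2 asks that 20% of the variance in the change of the psychological target, given in brackets as ETB and IAT with no connective, "must be associated with amygdala or dACC to mPFC FC changes during the ESOM or ER tasks after NF".

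Other sections bear on how this is read:
- **Scores (Section 5).** The IAT score has a defined sign: "A positive IAT score indicates stronger association between death and self". The ETB has four tasks. For the face-recognition test, "It yields accuracy and reaction times across positive and negative expressions"; for the recall task, "Recall accuracy and intrusions of positive vs. negative descriptors are the outcomes". The categorisation and dot-probe tasks add further outcomes. No composite or primary ETB score is named.
- **Visit (Section 5, Table 1).** IAT and ETB are scheduled after training at both Visit 4 and Visit 5.
- **Sample (Section 18, Power Analysis).** "With N=40 (20 per NF's loci").
- **Analysis (Section 18).** The paragraph on links with psychological targets says only that extracted FC is correlated with ETB and IAT change. The Data Analysis Plan says that puberty, severity, "treatment indexes, substance use, IQ, handedness, or any variable differing between key groups will be covariates in all analyses". Section 19.7 adds: "We must include age in all analysis to control for developmental differences in brain maturation".
- **Locus for R33 (Section 4).** One locus goes forward, chosen on engagement and functional improvement in R61.

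**The concern.** Milestone 2 is a bare observed R-squared with two alternatives for locus and two for task. It has no required direction, no significance condition and no requirement that the locus be the one that met Milestone 1. Read literally, it can be met by an association in the wrong direction, or at a locus that training did not engage. The 3dClustSim threshold in Section 18 applies to imaging maps, not to these correlations.

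The milestone matters most when training does move the brain targets but that movement has nothing to do with behaviour. Milestone 1 is then likely to be met, and only Milestone 2 can reveal the missing link that R33 Aim 2 relies on. If chance often satisfies it, a go decision rests on weak evidence of mechanism.

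**Working it through.** The plan gives no chance-pass rate or power for Milestone 2, so there is no figure to reproduce. Its 80% power at d=0.49 concerns effect sizes only.

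**Inputs from the plan.** R-squared cut 0.20; n=20 per locus; two loci; two tasks; six named covariates (puberty, severity, treatment, substance use, IQ, handedness), seven with age.

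**Assumptions not in the plan.** Normal data; correlation 0.3 between the two tasks' FC changes; correlation 0 to 0.7 between scores; activity drawn independently of FC change and behaviour.

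**1. One look.** With no association and k covariates, R-squared follows Beta(1/2, (n−2−k)/2). P(R-squared ≥ 0.20) is:
- n=20: 4.8% (k=0), 10.9% (k=6), 12.5% (k=7)
- n=40, k=0: 0.38%

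**2. Milestone 2 alone, n=20, raw r.** If looks were independent:
- one locus, either task, one score: 1 − 0.952² = 9.4%
- either locus, either task, one score: 1 − 0.952⁴ = 17.9%
- either locus, either task, either of two scores: 1 − 0.952⁸ = 32.6%

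Simulation with correlated tasks and scores gives about 17% for one score and 28–32% for either of two. For a single locus the figures are about 9% and 15–17%. If the IAT and one ETB summary must both pass, the rate is 3–7%. Requiring the expected sign roughly halves the one- and two-score rates.

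**3. Pooled, n=40, raw r.** Two to eight looks at 0.38% give 1 − 0.9962² = 0.8% up to 1 − 0.9962⁸ = 3.0%, so about 1–3%.

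**4. Both milestones.** Milestone 1 is modelled as observed d ≥ 0.4 for activity and for FC in at least one task, at the same locus. Under pure noise it passes in 0.7–0.8% of runs, so both milestones pass in under 1%.

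Now let activity and FC truly rise (d=0.5 each, assumed) with FC change unrelated to behaviour. Milestone 1 passes 82% of the time. For normal data the sample correlation is independent of the sample means and SDs, so passing Milestone 1 leaves the raw chance rate unchanged: 0.82 × 0.175 ≈ 14% for one score. Simulated joint rates:

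| Rule | One score | Either of two |
|---|---|---|
| As written, any locus | 14–15% | 23–27% |
| Same locus meets both milestones | 10% | 17–19% |
| Same locus and expected sign | about 5% | about 9% (half of 17–19%) |
| Any locus, Milestone 1 also needs p<0.01 | about 5% | about 8% |

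The last row approximates the imaging threshold by an ROI t-test. Two-sided p<0.01 at n=20 needs d ≥ 2.861/√20 = 0.64, which passes 26.3% of the time. Then 0.263 × 0.175 = 4.6%, and 0.263 × 0.30 to 0.32 = about 8%.

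With the plan's pilot activity effects (0.37 and 0.324) and FC d=0.4 (assumed), Milestone 1 passes 51–52% of the time and both pass about 9% (one score) or 16% (two).

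**The case against.** **These are not error rates for the go decision.** This stands. A reader might infer that R33 would open on noise 17% or 30% of the time. The plan does not support that, because both milestones are required and Milestone 1 stops pure noise. Section 18 also attaches a corrected 0.01 threshold to the activity tests and similar thresholds to FC. If these are part of Milestone 1, the joint rates fall to about 5% and 8%.

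**Section 4 implies one carried locus.** This largely stands and roughly halves the Milestone 2 rates. But Section 4 describes the choice of R33 locus, and Section 1 does not make a common locus a condition of passing.

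**The sample may not be 20 per locus.** Section 11.1 calls 60 participants the minimum for analysis, yet still gives 20 data sets per target, as does Section 29.1. If 60 meant 30 per locus (an assumption), a single look passes 1.3% of the time and four or eight independent looks give about 5% and 10%. Pooling lowers the rate further. That the answer moves this much is itself a reason to state the reading.

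**Covariates are already settled by the wording on all analyses.** Arguable, but the paragraph on these correlations mentions no adjustment and the 20% statistic is undefined. The two places need reconciling.

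**Stronger readings.** Letting any of eight scores count (the IAT plus seven ETB outcomes) would give 56–79% for Milestone 2 alone. Section 1 names the ETB as a battery and does not say that any sub-score suffices, so this is not a fair headline. A false efficacy claim is not in prospect either: R33 retests Aim 2 in 70 randomised participants.

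**Conclusion.** The point holds as a defect in the decision rule and should be fixed. Milestone 2 can be met in the wrong direction or at the wrong locus, and its score, visit, combination rule, analysis unit and form of R-squared are open.

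Where it is most needed, with brain targets engaged but unrelated to behaviour, both milestones pass by chance about 14–15% of the time with one score and 23–27% with either of two. With a common locus this becomes 10% and 17–19%; with a p<0.01 condition on Milestone 1, about 5% and 8%. These figures rest on n=20 per locus, raw r, d=0.5 and the assumed task and score correlations. The one- and two-score rates depend little on those correlations but a great deal on per-locus versus pooled analysis. The consequence is a go decision on weak evidence of mechanism.

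**What to change.** Before R61 outcomes are examined, add a paragraph to the milestones that:
1. requires the association to have the expected sign, which can be inferred from Milestone 1 and H2.1;
2. requires the same locus to meet both milestones, consistent with Section 4;
3. names the IAT or one pre-defined ETB composite, or states that both must pass, and names one post-training visit;
4. states per-locus or pooled analysis, and raw or partial R-squared with a short fixed covariate list;
5. reports all other scores as exploratory.

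If partial R-squared is chosen, report a permutation p-value with it, because at n=20 chance alone reaches 20% in 11–13% of single looks with six or seven covariates.

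Both tasks can stay and the 20% cut need not rise. Items 1 and 2 alone reduce the one-score joint rate from about 15% to about 5%. Restricting the milestone to one task, raising the cut or adding a maximum-statistic threshold would lower the rate further but cost power, so these are optional.

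The cost is some wording, plus a short permutation script if covariates are used. The milestone becomes somewhat harder to pass: a single named raw pair with the sign required passes 52%, 73% and 88% of the time when the true R-squared is 0.20, 0.30 and 0.40. Nothing in the conduct of the study changes.
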